3.2.4 Pharmacokinetic and anti-drug antibody assessments

Blood samples will be collected to determine the PK profile of nemolizumab and to assess anti-drug antibodies (ADA). The serum concentration of nemolizumab will be assessed at baseline, weeks 1, 2, 4, 8, 12, 16, 20, 24, 28, 32 and at any unscheduled visit for safety reasons. ADA will be assessed at baseline, weeks 4, 8, 16, 24, 32 and at any unscheduled visit for safety reasons. ADA assessment will include screening, confirmatory, titer, neutralizing antibodies (Nab) and IgE-based assays.

At the injection visits (baseline, weeks 4, 8, 12, 16 and 20), PK samples will be collected within 30 minutes before drug injection (pre-dose samples); At weeks 1, 2, 24, 28 and 32, blood samples will be collected at the usual time of drug injection with an allowed time window of ± 1 h.

Results will be described in the bioanalytical report, which will be included as an appendix in the final clinical study report.

PK parameters will be determined by a model independent approach (non-compartmental analysis [NCA]) using individual serum concentration values. The details surrounding NCA analysis will be covered under a separate PK Analysis Plan. When appropriate, the following PK parameters will be determined for each subject:

From baseline to week 4:

- C_{\max} : The observed peak drug concentration
- T_{\max} : The time at which C_{\max} occurs
- AUC_{0-28d} : Area under the concentration time curve from pre dose through approximately 28 days post dosing. AUC_{0-28d} will be calculated by mixed linear logarithmic trapezoidal method. AUC_{0-28d} includes the serum drug concentration up to week 4 (i.e. the serum concentration collected at baseline, week 1, 2 and 4).

From baseline to week 12:

- AUC_{0-12w} : Area under the concentration time curve from pre dose through 12 weeks post dosing. AUC_{0-12w} will be calculated by mixed linear logarithmic trapezoidal method. AUC_{0-12w} includes the serum drug concentration up to week 12 (i.e. the serum concentration collected at baseline, week 1, 2, 4, 8 and 12).

From baseline to week 24:

- AUC_{0-24w} : Area under the concentration time curve from pre dose through 24 weeks post dosing. AUC_{0-24w} will be calculated by mixed linear logarithmic trapezoidal method. AUC_{0-24w} includes the serum drug concentration up to week 24 (i.e. the serum concentration collected at baseline, week 1, 2, 4, 8, 12, 16, 20 and 24).

From week 20 to week 32:

- AUC_{0-t} : Area under the concentration time curve calculated by the mixed linear logarithmic trapezoidal method from the last administration (week 20) up to the sampling time corresponding to the last quantifiable concentration (C_{last}).

- AUC_{0-inf} : Area under the plasma concentration time curve calculated by the mixed linear logarithmic trapezoidal method from the last administration (week 20) and extrapolated to time infinity
- $t_{1/2}$: the terminal half-life value ($t_{1/2}$) will be calculated using the equation $\ln 2/k$ after the last drug injection (week 20).

At weeks 4, 8, 12, 16, 20, 24, 28, 32:

- C_{trough} : The residual drug concentration (pre-dose level).
- Accumulation index: calculated with the serum nemolizumab trough concentration obtained 4 weeks after the first dose (week 4) and 4 weeks after last drug injection (week 24).

ADA will be evaluated using a validated ELISA screening assay. If serum circulating ADA is detected, they will be characterized using a validated assay. ADA assessment will include screening, confirmatory, titer, neutralizing antibodies (Nab) and IgE-based assays.

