4.9 Other Analyses

4.9.1 Pharmacokinetic parameters and anti-drug antibody analyses

The PK parameters derived using non-compartmental techniques will be regarded as primary endpoints for the PK analyses (see Section 3.2.4). Primary inference for all the PK parameters will be based on the PKAP population.

Descriptive statistics (n, arithmetic mean, SD, minimum, median, maximum) by treatment group will be calculated for all derived PK endpoints. When calculating the statistics on PK parameters, if the values of more than half of the measured subjects are BLQ, the statistics will not be summarized for that measurement time point, and NC (Not Calculated) will be displayed. Geometric means and between-subject coefficients of variation (CVb) will be calculated for log_e-transformed AUC_{0-28d}, AUC_{0-12w}, AUC_{0-24w}, AUC_{0-t}, AUC_{0-inf}, C_{trough} and C_{max} where:

where: SD is the standard deviation of the \log_e -transformed data.

Following \log_e -transformation, AUC_{0-28d} , AUC_{0-12w} , AUC_{0-24w} , AUC_{0-t} , C_{trough} and C_{max} will be analyzed separately using analysis of variance (ANOVA), fitting a model with treatment group as a fixed effect. The residual variance from the model will be used to calculate point estimates and 90% CIs for the least squares means for each treatment formulation on the \log_e scale. These estimates will be back transformed to give point estimates and 90% CIs on the original scale.

The concentration at each time point will be summarized as arithmetic mean, SD, median, minimum, and maximum, number of BLQs (Below the Limit of Quantification). PK parameters using geometric means will be compared to determine when steady state conditions are achieved during the treatment period.

The potential relationship between serum concentrations of nemolizumab and change in EASI, pruritus NRS, or other indicators of disease activity will be explored using PK/Pharmacodynamics (PD) modeling, as appropriate.

The following Exposure-Response analysis will be performed:

- Percent change in EASI vs individual serum concentrations (scatter plots):
 - at Week 4
 - AUC_{0-28d}
 - C_{trough} week 4
 - at Week 12
 - AUC_{0-12w}
 - C_{trough} week 12
 - At week 24
 - AUC_{0-24w}
 - C_{trough} week 24

- Percent change in weekly average of the peak pruritus NRS vs individual serum concentrations (scatter plots):
 - at Week 4
 - AUC_{0-28d}
 - C_{trough} week 4
 - at Week 12
 - AUC_{0-12w}
 - C_{trough} week 12
 - At week 24

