 - AUC_{0-24w}
 - C_{trough} week 24

- Percent change in sleep disturbance NRS vs individual serum concentrations (scatter plots):
 - at Week 4
 - AUC_{0-28d}
 - C_{trough} week 4
 - at Week 12
 - AUC_{0-12w}
 - C_{trough} week 12
 - At week 24
 - AUC_{0-24w}
 - C_{trough} week 24
- Proportion of subjects achieving IGA success (defined as IGA 0 [Clear] or 1 [Almost Clear]) vs quartile of concentrations (bar plots):
 - at Week 12
 - AUC_{0-12w}
 - C_{trough} week 12
 - At week 24
 - AUC_{0-24w}
 - C_{trough} week 24
- EASI-75 response rate vs quartile of concentrations (bar plots):
 - at Week 12
 - AUC_{0-12w}
 - C_{trough} week 12
 - At week 24
 - AUC_{0-24w}
 - C_{trough} week 24
- Incidence of TEAEs in subjects treated with nemolizumab categorized by steady state trough serum concentration in 4 quartiles.

Incidence of positive ADA results will be summarized and plotted by treatment group (absolute occurrence and percent of subjects) at each visit. Incidence of treatment-related positive ADA (subjects who will become ADA positive only after Nemolizumab administration) will also be summarized and plotted by treatment group (absolute occurrence and percent of subjects) at each visit.

An interim PK and Exposure-Response analysis will be done with the bionalytical data available at Week 24 analysis (see Section 4.7.1.5). The interim analysis will include:

- Serum pharmacokinetic parameters will be listed by cohort, subject and day, and summarized by treatment.
- Serum Nemolizumab concentrations will be plotted by treatment group (individual PK profiles, mean PK profile)

- Descriptive statistics for calculated PK parameters will include: n, arithmetic mean, SD, median, minimum and maximum values.
- Geometric mean, geometric coefficient of variation (CVb), lower quartile (Q1), and upper quartile (Q3) will be presented for AUC_{0-28d} , AUC_{0-12w} , AUC_{0-24w} , AUC_{0-t} , C_{trough} and C_{max} . PK parameters will also be summarized by weight category. Analysis of PK parameters, AUC_{0-28d} , AUC_{0-12w} , AUC_{0-24w} , AUC_{0-t} , C_{trough} and C_{max} , using an analysis of variance (ANOVA) will be presented.
- The Exposure-Response analysis described above.
- Incidence of positive ADA results on individual PK profiles (plot with 3 different identifications for the negative ADA, for the treatment-related positive ADA and for the positive ADA).

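### The trapezoidal AUCs that extend beyond week 4 miss every later peak, so AUC0-12w, AUC0-24w and the week-20 AUCs will understate exposure, most of all at 90 mg for the first two

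*SAP*

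**What the plan says.** SAP 3.2.4 schedules PK samples at baseline and weeks 1, 2, 4, 8, 12, 16, 20, 24, 28 and 32. On timing it states: "At the injection visits (baseline, weeks 4, 8, 12, 16 and 20), PK samples will be collected within 30 minutes before drug injection". Week 24 falls 28 days after the final injection.

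From these samples the SAP defines, by mixed linear-log trapezoid:

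- AUC0-28d and AUC0-12w, each with its own sample list;
- AUC0-24w, with the list "i.e. the serum concentration collected at baseline, week 1, 2, 4, 8, 12, 16, 20 and 24";
- AUC0-t, running "from the last administration (week 20) up to the sampling time corresponding to the last quantifiable concentration";
- AUC0-inf, which starts at week 20 in the same way and is extrapolated.

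It adds: "The details surrounding NCA analysis will be covered under a separate PK Analysis Plan".

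SAP 4.9.1 says: "The PK parameters derived using non-compartmental techniques will be regarded as primary endpoints for the PK analyses". On the log scale, each parameter on a stated list "will be analyzed separately using analysis of variance (ANOVA), fitting a model with treatment group as a fixed effect", giving LS means with 90% CIs. That list holds Cmax, Ctrough and four AUCs (AUC0-28d, AUC0-12w, AUC0-24w, AUC0-t). AUC0-inf is summarised but is not in that model list. AUC0-12w and AUC0-24w are also axes of exposure-response plots at weeks 12 and 24. Most of this recurs early: "An interim PK and Exposure-Response analysis will be done with the bionalytical data available at Week 24 analysis".

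Protocol 7.3.2 lists AUC0-t for weeks 20-32, but not AUC0-12w, AUC0-24w or AUC0-inf. SAP 4.11 records only efficacy endpoint changes.

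**The concern.** A trapezoid sees only what lies on or between its sample points. Weeks 1 and 2 are the only scheduled samples inside a dosing interval. From week 4 to week 24 the calculation joins one trough to the next. Protocol 3.4 puts the peak 4 to 9 days after a dose and about three times the trough, so the rise and fall between troughs is left out. The error can only be downward.

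It also differs by arm. The 10 and 30 mg arms have a doubled first dose, so more of their exposure falls in the one interval sampled after the dose. The 90 mg arm does not, so its AUC0-12w and AUC0-24w are understated more.

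At stake are the absolute exposure figures. PK characterisation is a secondary objective, and narrow 90% CIs would surround values well below true exposure. The AUC axes of the exposure-response scatter plots would be too low, and compressed at 90 mg.

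**Working it through.** **Inputs from the documents.** Half-life around 2 weeks, Tmax 4-9 days, dose-proportional concentrations, and peak-to-trough fluctuation of 3 (Q4W) and 1.5 (Q2W): all Protocol 3.4. Doses on days 0, 28, 56, 84, 112 and 140, with the first doubled for 10 and 30 mg. Sample days 0, 7, 14, 28, 56, 84, 112, 140, 168, 196 and 224.

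**Assumptions.** One compartment with first-order absorption; half-life 14 days, with 12-18 days as sensitivity.

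**Formulas.** ke = ln 2 / 14 = 0.0495 per day. ka solves Tmax = ln(ka/ke)/(ka − ke): 0.718, 0.351 and 0.210 per day for Tmax 4, 6.5 and 9 days. One maintenance dose (scaled to dose/volume = 1) gives c(t) = ka/(ka − ke) × (exp(−ke t) − exp(−ka t)), and doses are superposed. Trapezoid: Δt(c1 + c2)/2 when rising, Δt(c1 − c2)/ln(c1/c2) when falling. True AUC is the exact integral.

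**Check against the protocol's own figure.** Half-life 14 days with Tmax 4-5 days gives fluctuation of 2.9-3.1 (Q4W) and 1.5-1.6 (Q2W), matching the stated 3 and 1.5. Tmax 9 days gives 2.2 for Q4W, so the low ends below come from the part of the grid that agrees least with the protocol.

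**Worked case: 90 mg, Tmax 6.5 days.** Sampled concentrations on days 0 to 168: 0, 0.723, 0.574, 0.291, 0.364, 0.382, 0.387, 0.388, 0.388. For example, days 28-56 give 28 × (0.291 + 0.364)/2 = 9.17, against a true 18.73.

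- Trapezoid: 2.53 + 4.52 + 5.83 + 9.17 + 10.44 + 10.76 + 10.84 + 10.86 = 64.95
- True: 3.85 + 4.61 + 5.86 + 18.73 + 19.83 + 20.11 + 20.17 + 20.19 = 113.35
- AUC0-24w: 64.95/113.35 = 0.573, or 42.7% low
- First interval alone: 12.88/14.32, or 10.0% low
- Five later intervals: 52.07/99.03, or 47.4% low

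**Full grid, percent low (Tmax 4-9 days):**

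| Parameter | Half-life 14 d: 10 and 30 mg | Half-life 14 d: 90 mg | Half-life 12-18 d: 10 and 30 mg / 90 mg |
|---|---|---|---|
| AUC0-12w | 24.7-33.3 | 33.7-42.7 | 22.4-36.2 / 30.8-46.2 |
| AUC0-24w | 31.6-40.9 | 37.2-46.9 | 27.8-45.1 / 32.8-51.4 |
| Week-20 AUC0-t, week 32 quantifiable | 28.5-37.7 | same | 22.1-44.6 |
| Week-20 AUC0-t, week 28 last | 30.2-39.7 | same | 24.3-46.2 |
| Week-20 AUC0-t, week 24 last | 40.0-50.4 | same | 34.0-56.2 |
| AUC0-inf, week 32 quantifiable | 27.9-37.1 | same | 21.1-44.2 |
| AUC0-28d | 7.4-15.2 | same | 7.1-16.1 |

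The three AUC0-t rows are needed because that AUC stops at the last quantifiable sample and Protocol 3.3 expects levels below the LOQ at study end. AUC0-28d is low because its first post-dose sample is day 7.

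Keeping only half-life/Tmax pairs with fluctuation 2.7-3.3 gives AUC0-12w 29-34% / 39-44%, AUC0-24w 38-42% / 43-49%, and AUC0-t 32-42% with week 32 quantifiable.

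**Between arms, half-life 14 d, Tmax 4 d.** (100 − 42.7)/(100 − 33.3) = 0.86 for AUC0-12w, so the 90:30 mg ratio is understated by 14%. Over Tmax 4-9 days the range is 12-14%, and 8-10% for AUC0-24w.

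**Check without a compartment model.** Take trough 1, peak 3, a linear rise to day d and a log-linear fall: area = 2d + (28 − d) × 2/ln 3, which is 51.7 for d = 4 and 52.6 for d = 9. Joining the troughs gives 28, or 53-54% of the interval's AUC.

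**The case against.** **Little that is tested depends on these AUCs.** This stands and sets the scope. The ANOVA gives per-arm LS means, with no between-arm contrast and no dose-proportionality test stated. Each AUC plot has a Ctrough companion, and adverse events are grouped by trough quartile. In a simulation with assumed variability (log-SD 0.2 for half-life and 0.4 for volume, Tmax 4-9 days, 15% residual error), ranking by the trapezoidal AUC0-12w and AUC0-24w correlated 0.99 with true ranking overall and 0.96-0.98 within arms. There, 89-91% of subjects stayed in their true quartile.

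**Other exposure-response work is planned.** This also stands. Protocol 9.1.5.4 and SAP 4.9.1 foresee PK/PD modelling of concentrations, and the protocol synopsis plans exposure-response modelling of week-24 EASI and week-4 pruritus NRS. That work does not correct the ANOVA summaries, but the AUC plots are not the only evidence.

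**The PK Analysis Plan may qualify or withhold these AUCs.** It was not available, so nobody can say that they will be reported uncorrected. But the SAP fixes both the samples and the method, and its general proviso that parameters are derived where appropriate sets no criterion for withholding them. Unscheduled safety samples could fall inside an interval, but they are not in the AUC0-12w or AUC0-24w lists.

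**The size rests on a model.** Correct: 12-18 days is an assumed range around the protocol's 2 weeks. The direction does not depend on it.

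**Conclusion.** The concern holds, with limited reach. The downward direction follows from the sampling days and the protocol's own peak timing, and is firm. The size is less certain because it depends on the one-compartment assumption: about 25-47% low for AUC0-12w and AUC0-24w across arms at a 14-day half-life, and 28-50% for week-20 AUC0-t depending on the last quantifiable sample. For the later AUCs together, half-lives of 12-18 days give about 21-56%. AUC0-28d shares the problem in milder form.

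Affected are the absolute summaries (LS means with 90% CIs for AUC0-12w, AUC0-24w and AUC0-t; descriptive AUC0-inf) and the AUC axes of the week-12 and week-24 scatter plots.

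A reader might infer that the dose-response conclusion, the exposure-response programme or dose selection is compromised. The documents do not support that. The primary efficacy analysis and MCP-Mod use no AUC, ranking and quartile displays are little affected, Ctrough outputs are unaffected, and concentration-based modelling is planned separately. The point should be corrected, but it threatens no primary result.

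**What to change.** In SAP 3.2.4 and 4.9.1:

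- Restrict non-compartmental AUC reported as exposure to AUC0-28d, with a note that it is modestly low because the first post-dose sample is day 7.
- Label AUC0-12w, AUC0-24w and the week-20 AUC0-t and AUC0-inf as trough-based indices that are not reported as exposure, including in the interim PK output.
- Rely on the Ctrough outputs already planned.
- Record the change in SAP 4.11 or by amendment, naming the departure from Protocol 7.3.2 for week-20 AUC0-t. The other three AUCs are not on the protocol's list. Align the PK Analysis Plan.

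Optionally, also report model-based AUC0-12w, AUC0-24w and week-20 AUCs from the existing population PK model, after checking its fit to this trial's data. This is a preference. It departs from the model-independent method in Protocol 7.3.2 and 9.1.5.4, and later peaks would be inferred rather than observed.

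The minimum fix costs wording only, with no extra samples or visits. Its downside is that no headline non-compartmental AUC remains beyond week 4. The optional step adds time for model fitting and checking.

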3.4 Rationale for dosage and dose regimen

The PK and pharmacodynamics (PD) profile of nemolizumab was evaluated in two clinical trials, in which single doses from 0.1 to 3 mg/kg, or repeated doses of 0.1 mg/kg, 0.5 mg/kg or 2.0 mg/kg Q4W, or 2 mg/kg Q8W were studied. PK assessment after subcutaneous injections of mg/kg doses showed a dose proportional increase of nemolizumab serum concentrations after single and repeated dose administrations. The terminal elimination half-life of nemolizumab was around 2 weeks after single and repeated administrations. Steady state concentrations were achieved from week 16 of treatment and limited systemic accumulation was observed after repeated administrations.

PK data were used to develop a population PK model that allows an accurate simulation of nemolizumab serum concentrations with different doses and dosing regimens.

Based on the results of the previous clinical studies, pruritus VAS endpoint was fitted to an indirect turnover model with placebo effect and maximum inhibition (I_{max}) equation; the concentration causing 50% inhibition (IC_{50}) of the effect on VAS was estimated at 0.66 $\mu\text{g/mL}$ (Bootstrapped 90% CI from 0.276 $\mu\text{g/mL}$ to 1.93 $\mu\text{g/mL}$). The concentration causing 90% inhibition (IC_{90}) was estimated at 5.96 $\mu\text{g/mL}$.

The doses and dose regimen were selected based on the rationale described below:

- Dose:
 - Fixed doses vs mg/kg doses: In this study, the administered dose will not be adjusted to the body weight of the individual subject. Fixed dosing was selected because nemolizumab demonstrated a large therapeutic window between 0.5 and 2.0 mg/kg and a low inter-individual variability in systemic exposure (CV 30%) in the previous phase 2a study, with no sign of dose related toxicity after single administrations of up to 3mg/kg in the previous phase 1 study. The population PK model demonstrated a limited body weight effect compared to the variability in the effect on VAS. The administration of fixed doses was considered as similar to mg/kg doses over a wide range of body weights (from 30 to 150 kg). This fixed dose selection can also avoid errors that could be made in calculating, preparing, and administering a weight-based dose.

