 - Dose selection: The population PK model was used to simulate systemic exposure using several fixed doses. The simulations using 10, 30 and 90 mg monthly doses provided a range of well-distributed systemic exposures on the expected exposure-response curve, with a plateau of effect at or below 90 mg. Simulation results show that the proposed fixed doses of 10, 30 and 90 mg are expected to provide similar efficacy outcomes as weight-based dosing with 0.13, 0.4 and 1.2 mg/kg, respectively (assuming a mean body weight of 75kg). These fixed doses are expected to result in systemic exposure levels in a similar range to those observed in the previous Phase 2a study (Table 3). The overall good safety profile of nemolizumab was confirmed with a single dose of up to 3 mg/kg and repeated doses of up to 2 mg/kg Q4W for up to 64 weeks. The highest dose selected for this clinical trial is 90 mg, which corresponds to at most 2 mg/kg (as subjects with a body weight <45 kg will be excluded from the study).

- Loading dose: Subcutaneous administration of nemolizumab resulted in slow absorption with peak serum concentrations achieved after 4 to 9 days. Plateau systemic exposure levels should be achieved after at least 8 weeks of repeated monthly administrations. Therefore, loading doses are necessary to rapidly achieve targeted systemic levels, and to ensure a fast onset of action. Rapid inhibition of pruritus in AD is an important treatment goal in itself, and is also expected to contribute to breaking the itch-scratch cycle and thus to improve the skin condition in AD patients. Loading doses were simulated using the above-described PK model. To achieve targeted steady state systemic concentration levels from the first injection, loading doses of 20 mg and 60 mg are needed for the 10 and 30 mg groups, respectively. The 90 mg dose will be administered without a loading dose, as it is expected to provide systemic exposure that is high enough to achieve the maximum inhibitory effect from the first drug administration.

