3 INVESTIGATIONAL PLAN

3.1 Overall Study Design and Plan

This is a randomized, placebo-controlled, double-blind, parallel-group, dose-ranging, phase 2b study to evaluate the efficacy and safety of various doses of nemolizumab in moderate-to-severe AD subjects with severe pruritus. The duration of this clinical trial is up to 36 weeks for a given subject, including a 2 to 4-week run-in period, a 24-week treatment period and an 8 week follow-up period (12 weeks after the last study drug administration).

Eligible subjects must have moderate-to-severe AD, severe pruritus and a documented history of inadequate response to topical AD medications. Subjects meeting the inclusion/exclusion criteria at the screening visit will receive background therapy of AD (including a moisturizer, a medium potency TCS for the body, and a low potency TCS for the face, neck etc.) to be used throughout the study. Subjects who still meet the inclusion/exclusion criteria at the baseline visit will be randomized in a 1:1:1:1 ratio to either of the 3 groups of nemolizumab or placebo. Randomization will be stratified by AD severity based on the baseline Investigator's Global Assessment (IGA) scores (3 or 4). Injection of study drug will occur every 4 weeks (Q4w, at weeks 4, 8, 12, 16 & 20). A loading dose will be administered on day 1 for the groups of 10 mg and 30 mg only (20 mg and 60 mg, respectively), while for 90 mg group, the same dose will be administered at each injection visit.

An independent Data Monitoring Committee (IDMC) will be set-up to monitor safety data generated in this clinical trial on an ongoing basis and make appropriate recommendations to the sponsor.

Assessments of efficacy, safety and PK will be conducted throughout this clinical trial. Refer to Appendix 1 for the complete schedule of assessments.

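### The SAP's accumulation index has no dose adjustment; as a plain week-24/week-4 trough ratio it would be about half the true value in the two loading-dose arms

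*SAP*

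**What the plan says.** SAP section 3.2.4 lists the accumulation index among the PK parameters to be determined, where appropriate, for each subject. The whole definition is that it is "calculated with the serum nemolizumab trough concentration obtained 4 weeks after the first dose (week 4) and 4 weeks after last drug injection", the latter being the week-24 visit. No operator, direction or dose handling is given, and no arm is treated differently.

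The same section fixes the sampling time. At injection visits "PK samples will be collected within 30 minutes before drug injection (pre-dose samples"), so the week-4 value reflects the day-1 dose alone. SAP section 3.1 states that "A loading dose will be administered on day 1 for the groups of 10 mg and 30 mg only (20 mg and 60 mg, respectively"), whereas the 90 mg arm receives the same dose throughout.

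SAP section 4.9.1 says that descriptive statistics "by treatment group will be calculated for all derived PK endpoints", which takes in the index. It adds nothing to the definition, and the PK parameter list in protocol section 7.3.2 does not contain the index. Section 3.2.4 also says: "The details surrounding NCA analysis will be covered under a separate PK Analysis Plan".

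**The concern.** An accumulation index is meant to show how far exposure builds up when the same dose is repeated. Its two inputs must then come from the same dose, or be put on the same dose scale. Here they do only at 90 mg. In the 10 and 30 mg arms the earlier trough follows double the maintenance dose, so a plain ratio of the two troughs mixes accumulation with the size of the loading dose.

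A table by treatment group would set two arms with a halved index beside one with an undistorted index. A reader could conclude that accumulation depends on dose, against the dose proportionality reported in protocol section 3.4. Characterising the PK profile is a secondary objective, so such a statement could reach the study report.

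**Working it through.** The documents state no value for the index, so there is no planned figure to reproduce. The check asks what a week-24/week-4 ratio would return in each arm if the kinetics were identical.

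**Inputs**
- Doses on day 0 and then every 28 days to day 140: 20 mg then five of 10 mg; 60 mg then five of 30 mg; six of 90 mg (SAP 3.1).
- Troughs at day 28 (before the second dose) and day 168 (SAP 3.2.4).
- Linearity: earlier studies "showed a dose proportional increase of nemolizumab serum concentrations after single and repeated dose administrations" (protocol 3.4), so contributions of successive doses add up. The simulated means in protocol Table 3 agree: 3.53/1.20 = 2.94 and 10.84/1.20 = 9.03 for dose ratios of 3 and 9.
- Half-life: "The terminal elimination half-life of nemolizumab was around 2 weeks after single and repeated administrations" (protocol 3.4), taken as 14 days. The range of 10 to 28 days is an assumption.
- Absorption: "slow absorption with peak serum concentrations achieved after 4 to 9 days" (protocol 3.4), run with peak times of 4, 6.5 and 9 days in a one-compartment model with first-order absorption.

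**Formulas.** Let r be the fraction remaining after one 28-day interval, r = 2^(−28/half-life). Once absorption is essentially complete:
- equal doses (90 mg): index = (1 − r^6)/(1 − r);
- first dose doubled (10 and 30 mg): index = r^5 + (1 − r^5)/(2(1 − r)).

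**At 14 days**, r = 2^(−2) = 0.25:
- 90 mg: (1 − 0.00024)/0.75 = 1.333;
- 10 and 30 mg: 0.00098 + 0.99902/1.5 = 0.667;
- loading arm / 90 mg = 0.667/1.333 = 0.500.

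**Range over half-life**, with the spread over the three peak times:

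| Half-life (days) | 10 and 30 mg, plain | 90 mg, plain | Ratio | 10 and 30 mg, dose-normalised |
|---|---|---|---|---|
| 10 | 0.584–0.589 | 1.168–1.179 | 0.500 | 1.168–1.179 |
| 14 | 0.667–0.669 | 1.333–1.337 | 0.500 | 1.334–1.338 |
| 18 | 0.759–0.760 | 1.513–1.515 | 0.502 | 1.518–1.519 |
| 21 | 0.831 | 1.651–1.652 | 0.503 | 1.661–1.662 |
| 28 | 1.000 | 1.969 | 0.508 | 2.000 |

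The last column divides the week-24 trough by the maintenance dose and the week-4 trough by the first dose, which doubles the plain value in the loading arms and leaves 90 mg unchanged. What remains of the difference from 90 mg is r^5, the residue of the loading dose at week 24. At 28 days that is 0.03125/1.969 = 1.6%, the largest in the range; at 14 days it is 0.00098/1.333 = 0.07%.

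**Plausibility of the model.** With a 14-day half-life and a 4-day peak it gives a steady-state peak-to-trough ratio of 3.1, against the 3-fold fluctuation stated in protocol section 3.4.

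**The case against.** The strongest reply is that the SAP gives no formula. It names two inputs and leaves NCA details to a PK Analysis Plan, where a dose adjustment may well be written down. It also has the parameters determined only where appropriate, which would let the analyst drop the index in the loading arms. This stands to the extent that nobody can say from these documents that a wrong number will be reported. It does not remove the gap. The SAP fixes the same inputs for all arms, and the general qualifier says nothing about loading doses. Turning the ratio round does not help either: at 14 days it gives 1/0.667 = 1.50 against 1/1.333 = 0.75, again a factor of two.

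A second reply is that protocol section 3.4 chose the loading doses by simulation to reach steady-state levels from the first injection, so the plain index might lie near 1 rather than at 0.67. That is a fair caution about absolute values, which here come from a simple model and not from the sponsor's population PK model. In this model the plain loading-arm index reaches 1.00 only at 28 days, and there the 90 mg index is 1.97, so the gap between arms remains.

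Finally, the index carries little weight. It is absent from the geometric-mean and ANOVA lists in SAP section 4.9.1, and the exposure-response analyses use AUC and trough concentrations. This is correct, and it limits the importance of the point. A plain ratio can also serve to describe whether loading met its aim, provided it is not labelled accumulation.

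**Conclusion.** The concern holds, as a minor point. On the usual week-24/week-4 reading, the index built from the SAP's stated inputs would be about half the true accumulation ratio in the 10 and 30 mg arms and correct at 90 mg. The factor of about one half (0.500 to 0.508) follows from the two-to-one first dose and hardly depends on half-life or absorption. The values 0.67 and 1.33 apply to a 14-day half-life only.

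The result rests on linear kinetics, which the protocol supports, and on the PK Analysis Plan not already specifying a dose adjustment, which cannot be checked here. The 90 mg index, Cmax, AUC, trough concentrations, half-life and all efficacy results are unaffected. Where concentrations in the loading arms do fall from week 4 to steady state, the fall is real; the error would lie in calling it accumulation.

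**What to change.** Add one sentence to SAP section 3.2.4 and mirror it in the PK Analysis Plan: accumulation index = (week-24 trough / maintenance dose) / (week-4 trough / first dose). Alternatively, report the index as accumulation for the 90 mg arm only. Keep observed, unadjusted concentrations in the steady-state comparison of SAP section 4.9.1, where the actual course is what matters. The cost is one sentence in each document. No new data are needed, and dosing is untouched.
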